5.3 Monitoring during therapy

The patient may receive induction chemotherapy before inclusion in the study, and is as such not part of the study. The patients cannot be included in the study before a plan has been worked out showing that curatively intended radiation is possible, and informed consent has been obtained (Fig. 1).

	Screening/ Baseline	Treatment Period Timing	Day 30-45 after stop of treatment
Informed Consent	x	-	-
Demographics	x	-	-
Medical history	x	-	-
Physical examination	x	Weekly	x
Body weight	x	Weekly	x
Laboratory ¹	x	Weekly	x
ECG	x	-	x
Lung functions test ²	x	-	x
Lung CO diffusion test	x	-	-
CT scan thorax and upper abdomen	x	-	x
Tumor measurements	x	-	x
PET-CT ³	x	-	-
CT scan brain ⁴	x ⁴	-	-
Performance Status (PS)	x	Weekly	x
Side effects ⁵	-	Recorded weekly	x
Study drug compliance ⁶	-	x	x
Smoking status	x	Recorded Weekly	x

¹ Hematology: Hemoglobin, WBC, granulocytes and platelet count, INR (Only for patients receiving warfarin or coumarin-derivative). Biochemistry: Alkaline phosphatase, Serum bilirubin, Serum creatinine, ALAT (SGPT), LDH. Only laboratory abnormalities linked to unexpected clinical symptoms will be documented in the CRF.

² FEV₁/FVC test. If neoadjuvant chemotherapy, the test must be performed after cessation of chemotherapy.

³ CT scans, PET CT scans per institutional standards, EBUS or mediastinoscopy may be accepted as mediastinal evaluation if PET-CT is not available

⁴ If no PET-CT available

⁵ Side effects to be recorded according to CTC version 3.0

⁶ Pharmacy log

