1.3 Tarceva

Tarceva (Erlotinib hydrochloride) is a quinazolinamide that inhibits the intracellular tyrosin kinase domain of the EGFR. It is formulated as immediate release tablets. Bioavailability of Erlotinib following a 150 mg oral dose is about 60% (and almost 100% if taken together with food) and peak plasma levels occur 4 hours after dosing. The median half-life is 36 hours, and the time to reach steady-state plasma concentration is 7-8 days (12). Smokers have a 24% higher rate of Erlotinib clearance. Erlotinib is metabolized by the liver cytochrome P450 system primarily by CYP3A4 which may be a cause of interaction with other drugs.

2. Objectives of the study

The trial is a phase II study of daily Tarceva combined with definitive radiotherapy in inoperable locally advanced non small cell lung cancer (stage IIB-IIIB).

The objective of the phase II trial is to examine Tarceva concomitant with curatively intended irradiation 66 Gy (2 Gy x 33 F, 5 F per week):

Primary endpoint

- Local failure free survival at 9 months after start of radiotherapy evaluated at CT scan.

[figure not shown]
Secondary endpoints

- Toxicity
- Local tumor control by CT-scan
- Overall response rate (CR + PR).
- Local tumor control at 9 months evaluated by PET-CT
- Overall survival
- Disease free survival
- Late toxicity

3. Study design and dosing regimen

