7.3 Potential drug interactions

Substances that are potent inhibitors of CYP3A4 activity (eg, ketoconazole) decrease Tarceva metabolism and increase Tarceva plasma concentrations. This increase may be clinically relevant as adverse experiences are related to dose and exposure; therefore, caution should be used when administering CYP3A4 inhibitors with Tarceva.

Substances that are potent inducers of CYP3A4 activity (eg, rifampin, phenytoin) increase Tarceva metabolism and significantly decrease Tarceva plasma concentrations.

INR elevations and/or bleeding events have been reported in some cancer patients taking warfarin while on Tarceva. Patients taking warfarin or other coumarin-derivative anticoagulants should be monitored regularly for changes in prothrombin time or INR. Tobacco smoking may diminish the plasma levels of Tarceva, and may diminish the effect of radiation and should be avoided during the study period.

8. Adverse events

An AE is defined as any untoward medical occurrence in a patient or clinical investigation patient administered a pharmaceutical product regardless of its causal relationship to the study treatment. An AE can therefore be any unfavourable and unintended sign (including an abnormal laboratory finding), symptom, or disease temporally associated with the use of medicinal (investigational) product.

The occurrence of an AE may come to the attention of study personnel during study visits and interviews of a study recipient presenting for medical care, or upon review by a study monitor.

Information to be collected includes event description, time of onset, clinician's assessment of grade, relationship to study product (assessed only by those with the training and authority to make a diagnosis), seriousness, action taken with study drug, outcome, and time of resolution/stabilization of the event. All AEs occurring while on study must be documented appropriately regardless of relationship. All AEs will be followed to adequate resolution. All AEs must be reported on CRF to sponsor in order to record them for a final report to the Danish Medicines Agency.

Any medical condition that is present at the time that the patient is screened should be considered as baseline and not reported as an AE. However, if it deteriorates at any time during the study, it should be recorded as an AE.

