8.1 Serious adverse events (SAEs)

An SAE is defined as an AE that meets one of the following conditions:

- Death during the period of protocol defined surveillance
- Life-threatening event (defined as a patient at immediate risk of death at the time of the event)
- An event requiring inpatient hospitalisation or prolongation of existing hospitalisation during the period of protocol defined surveillance with the exception of treatment-related enteritis or fatigue, leucopenia, thrombocytopenia or hospitalization due to treatment administration or other elective measures
- Results in congenital anomaly or birth defect
- Results in a persistent or significant disability/incapacity
- Any other important medical event that may not result in death, be life threatening, or require hospitalisation, may be considered a serious adverse experience when, based upon appropriate medical judgment, the event may jeopardize the patient and may require medical or surgical intervention to prevent one of the outcomes listed above. Examples of such medical events include allergic bronchospasm requiring intensive treatment in an emergency room or at home, blood dyscrasias or convulsions that do not result in inpatient hospitalisation, or the development of drug dependency or drug abuse.

In this study unexpected and related SAEs are defined as adverse reactions with at least a possible relationship to study therapy that are not consistent with the approved summary of product

characteristics (SPC) and which to their nature are serious. The SPC is available at:
www.emea.europa.eu

All SAEs will be recorded on the appropriate SAE CRF, followed through resolution by the investigator, and reviewed and evaluated by the Medical Monitor

Abnormal laboratory values and clinical adverse events will be reported as SAEs if they are graded higher than 3 on the CTC v3.0.

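### Footnote 1 in sections 5.3 and 5.4 keeps most laboratory abnormalities off the CRF, contradicting sections 8 and 8.1; where sites follow it, laboratory toxicity is undercounted

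*Protocol*

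**What the plan says.** The section 5.3 schedule has haematology and biochemistry at baseline, weekly during treatment and once 30 to 45 days after treatment stops. The section 5.4 schedule repeats them at 6, 9, 12, 18 and 24 months. Footnote 1 to the laboratory row carries the same restriction in both tables: "Only laboratory abnormalities linked to unexpected clinical symptoms will be documented in the CRF".

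Section 8 (Adverse events) defines its subject broadly: "An AE can therefore be any unfavourable and unintended sign (including an abnormal laboratory finding), symptom, or disease temporally associated" with use of the product. It then requires that "All AEs occurring while on study must be documented appropriately regardless of relationship" and that "All AEs must be reported on CRF to sponsor in order to record them for a final report to the Danish Medicines Agency".

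Section 8.1 adds a grade-based rule: "Abnormal laboratory values and clinical adverse events will be reported as SAEs if they are graded higher than 3 on the CTC v3.0". It also states that "All SAEs will be recorded on the appropriate SAE CRF".

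Section 2 lists toxicity and, separately, "Late toxicity" among the secondary endpoints, with no exclusion for laboratory toxicity. In section 5.3 a separate side-effects row has its own footnote: "Side effects to be recorded according to CTC version 3.0".

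**The concern.** The footnote makes CRF entry depend on an unexpected symptom. Sections 8 and 8.1 make it depend on whether the finding is an adverse event and on its grade. Many changes in blood counts, liver tests or creatinine cause no symptom, so the two rules diverge for an ordinary type of finding.

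At stake is the laboratory part of the secondary toxicity endpoint. Any loss runs in one direction, towards too little toxicity. The trial is also multicentre: section 6.4 expects 3 to 15 patients per site, so 57 patients need at least four sites (57 / 15 = 3.8). If some sites follow the footnote and others follow section 8, differences in laboratory toxicity between sites will partly reflect which rule they read. A later analysis plan cannot repair this, because it cannot tabulate values that never reached the CRF.

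**Working it through.** No arithmetic applies. The protocol states no figure for laboratory toxicity, and the point depends on no sample size, power or event count. The check is to take each kind of laboratory finding and see what each rule requires.

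| Laboratory finding that is an adverse event | Footnote 1 (5.3, 5.4) | Sections 8 and 8.1 | Compatible? |
|---|---|---|---|
| Any grade, tied to an unexpected symptom | Recorded | Recorded; also on the SAE CRF if above grade 3 | Yes |
| Grade 3 or lower, symptom-free or with expected symptoms only | Not recorded | Recorded on the CRF as an adverse event | No |
| Above grade 3, symptom-free or with expected symptoms only | Not recorded | Recorded on the SAE CRF | No, but section 8.1 names this case explicitly |

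1. **Does section 8 or 8.1 contain a symptom condition that would reconcile the rules?** No. Section 8 lists a laboratory finding alongside signs and symptoms, and section 8.1 uses grade alone.

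2. **Does the footnote act as a filter for clinical relevance?** Not as written. It mentions no grade, no judgement of significance and no action taken. Its only test is an unexpected symptom.

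3. **How far does the exclusion reach?** The footnote does not define what counts as unexpected. If the list in section 8.2 is the reference, nausea, vomiting, abdominal pain, fatigue, anorexia and infection are all expected with Tarceva. A raised bilirubin with nausea, or a low granulocyte count with infection, would then stay out of the CRF as well. The footnote also covers INR in patients on warfarin-type drugs, although section 7.3 names INR elevation as a reported problem with the combination.

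4. **Does any passage give precedence?** None found. For a symptom-free laboratory adverse event a site cannot obey both rules.

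5. **Which results depend on these data?** The primary endpoint is local failure free survival at 9 months on CT (section 2), which uses no laboratory data. The numeric interim limit is a rate above 15% of grade 4 pneumonitis or esophagitis (section 6.3), both clinical events. The other stopping trigger in section 6.3, unexpected severe toxicity, could in principle draw on laboratory findings, but values above grade 3 reach the sponsor through section 8.1. What remains exposed is the laboratory part of the secondary toxicity endpoints.

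**The case against.** The strongest reply is that the footnote may only be meant to spare sites from transcribing routine laboratory results, leaving the adverse event and SAE forms to section 8. It hangs on the laboratory row, whereas side effects have their own row, graded weekly by CTC v3.0 during treatment. A site that reads section 8 carefully would record everything that matters. This reading is plausible, but the footnote speaks of the CRF as a whole and of abnormalities, not of routine values, so the wording does not establish it. The side-effects row also helps less in follow-up, where its footnote in section 5.4 points to radiation sequelae.

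The reply does limit the consequences. A reader might infer four stronger things that the documents do not support:

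- **That laboratory toxicity will be absent altogether.** Section 8.1 gives values above grade 3 an explicit route to the SAE CRF, with prompt reporting to the sponsor. Findings tied to unexpected symptoms are captured under either rule.
- **That pauses of Tarceva under section 3.3 would have no recorded cause.** Those pauses are for drug-related toxicity. Such toxicity is an adverse event, and section 8 asks for grade, relationship and what was done with the study drug. The pharmacy log would also show an interruption, though not its reason.
- **That the interim safety decision is compromised.** Its numeric limit does not use laboratory data.
- **That a number of lost patients can be stated.** Assuming 5% to 10% of 57 patients have a symptom-free grade 3 or 4 abnormality gives about 3 to 6 (0.05 × 57 = 2.9; 0.10 × 57 = 5.7). The documents support no such rate, and the count ignores the SAE route for grade 4.

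**Conclusion.** The contradiction is explicit, appears in both schedules and is left unresolved. Where sites follow the footnote, abnormalities that are symptom-free or linked only to expected symptoms are not captured, chiefly those of grade 3 or lower. Laboratory toxicity is then undercounted, and rates may not be comparable between sites.

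The direction of the bias is certain under that condition. Its size cannot be derived, because it depends on how many sites follow the footnote and how often such abnormalities occur, and the protocol gives neither. The conclusion assumes only that at least some sites read the footnote as written. The point should be corrected, but it does not threaten the trial's main result.

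**What to change.** Delete the restriction from footnote 1 in both section 5.3 and section 5.4. Replace it with a statement along these lines: laboratory abnormalities that meet the adverse event or SAE definitions in sections 8 and 8.1 are recorded in the CRF with their CTC v3.0 grade, whether or not symptoms are present; this includes at least every value of grade 3 or higher and every value that leads to a change in study drug.

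That last clause is a floor and must not become a new threshold in section 8. Section 8 now requires all adverse events on the CRF, and limiting it to grade 3 and above would remove lower-grade laboratory events that it currently captures. The change concerns data capture only and alters no dose or treatment rule.

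The cost is minor extra data entry. The tests are already scheduled, so no additional sampling is needed.

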5.4 Follow-up

The patients will be followed until 5 years after the start of radiotherapy or to recurrent disease according to the follow-up schedule. After discontinuation in the study the patient will be followed according to local standard.

Follow up (± 1 month after start of RT)	6	9	12	15	18	21	24	30, 36, 42, 48, 54, 60
Medical history	x	x	x	x	x	x	x	x
Physical examination	x	x	x	x	x	x	x	x
Laboratory ¹	x	x	x	-	x	-	x	-
Lung function tests FEV ₁ /FVC	x	x	x	x ²	x	x ²	x	x
Lung CO diffusion test	-	x	-	-	-	-	x	-
Weight	x	x	x	x	x	x	x	x
CT scan of thorax and upper abdomen	x	x	x	x	x	x	x	x
Tumor measurements ³	x	x	x	x	x	x	x	-
PET-CT ⁴	-	x	-	-	-	-	-	-
Performance Status	x	x	x	x	x	x	x	x
Smoking status	x	x	x	x	x	x	x	x
Side effects ⁵	x	x	x	x	x	x	x	x

¹ Hematology: Hemoglobin, WBC, granulocytes and platelet count, INR (Only for patients receiving warfarin or coumarin-derivative). Biochemistry: Alkaline phosphatase, Serum bilirubin, Serum creatinine, ALAT (SGPT), LDH. Only laboratory abnormalities linked to unexpected clinical symptoms will be documented in the CRF

² FEV₁/FVC test.

³ RECIST criteria (appendix 2)

⁴ PET CT scans if available at the institution

⁵ Radiation sequelae

5.5 Tumor response criteria.

Although PET-CT is allowed, the tumor response will be evaluated according to RECIST-criteria (version 1.1) by CT-scans of thorax and upper abdomen (15). Suspected recurrent tumor locally or regionally should be verified by biopsy if appropriate.

6. Criteria for efficiency and data-analysis

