6.1 Statistical considerations

All calculations will be performed on the basis of intention to treat. 2 sided tests will be performed. Level of type 1 error is 5%.

6.2 Sample size calculation:

Observed local failure free survival rate after 9 months after initiation of radiation was 70% among 300 patients treated in Odense for NSCLC stage IIB-IIIB. The study will be designed to find local recurrence free survival of 80% at 9 months after initiation of radiation equivalent to about 6-7 months after finishing radiotherapy. A rate of 80% would be clinically interesting, and should be included in the confidence interval of the phase II trial at a power of 90%. This requires 57 patients to be included in the phase II trial.

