Appendix 4: Dosage guidelines for management of study drug related toxicities

Toxicity, CTC Grade	Study Drug Dosage Modification	Guideline for Management
Diarrhea		
Grade 1	None	Consider Loperamide (4 mg at first onset, followed by 2 mg every 2 – 4 hours until diarrhea free for 12 hours) Appropriate rehydration
Grade 2	None	Loperamide (4mg at first onset, followed by 2 mg every 2 – 4 hours until diarrhea free for 12 hours) Appropriate rehydration
Grade 3	Interrupt Tarceva™	Loperamide (4 mg at first onset, followed by 2mg every 2 – 4 hours until diarrhea free for 12 hours) and Interrupt Tarceva™ until resolution to Grade ≤ 1, and restart at reduced dose Appropriate rehydration
Grade 4	Discontinue Study	Loperamide (4 mg at first onset, followed by 2mg every 2 – 4 hours until diarrhea free for 12 hours) Appropriate rehydration
Rash		
Grade 1	None	Any of the following: minocycline ^a , topical tetracycline, topical clindamycin, topical silver sulfadiazine, diphenhydramine, oral prednisone (short course) at discretion of the investigator.
Grade 2	None	Manage as described above
Grade 3 (or intolerable Grade 2)	Dose reduction; dose can be re-escalated when rash is ≤ Grade 2	Manage as described above
Grade 4	Discontinue Study	Manage as described above

^a Recommended dose: 200 mg orally bid (loading dose) followed by 100 mg orally bid × 7–10 days.

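### Section 5.4 ends scheduled follow-up at any recurrence, leaving the month-9 CT after distant-only relapse, and survival and late toxicity after any recurrence, unprovided for

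*Protocol*

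**What the plan says.** Section 5.4 sets the end of protocol follow-up: "The patients will be followed until 5 years after the start of radiotherapy or to recurrent disease according to the follow-up schedule". No site of recurrence is named. The next sentence reads: "After discontinuation in the study the patient will be followed according to local standard".

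The primary endpoint in section 2 is "Local failure free survival at 9 months after start of radiotherapy evaluated at CT scan". The secondary endpoints there include "Overall survival" and "Late toxicity".

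The tables in 5.3 and 5.4 place CT of the thorax and upper abdomen at baseline, 30-45 days after treatment, and at months 6, 9, 12 and onward. Radiation sequelae are recorded at each follow-up visit to month 60.

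Section 6.1 adds: "All calculations will be performed on the basis of intention to treat". Section 6.5 promises to report the data of every included patient.

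In Appendix 4, the entry for grade 4 diarrhea and grade 4 rash is "Discontinue Study", in a column headed "Study Drug Dosage Modification".

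**The concern.** Ending follow-up at recurrence suits disease free survival, where the first recurrence is the event. It does not suit an endpoint that asks about the local site at a fixed later time, nor endpoints that run on past recurrence.

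Two scheduled CTs, the one 30-45 days after treatment and the one at month 6, come before month 9 and can show distant disease. A patient whose relapse is found there, with the chest still controlled, has reached the stopping rule before the primary assessment. Such patients are unlikely to be a random subset with respect to later local failure or death. Overall survival and late toxicity are affected more widely, because their scheduled collection ends with every recurrence, local or distant.

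At stake is a single-arm comparison of 57 patients with a historical 70%, where the gain sought is 10 points. A modest share of patients with unknown 9-month status could matter on that scale.

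**Working it through.** **1. Does the rule cover distant relapse?** Section 5.4 names no site. Section 5.5, on biopsy verification, limits itself expressly to local or regional recurrence. The protocol therefore names the site when it means one, and the plain reading of 5.4 is recurrence anywhere.

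**2. What is lost, endpoint by endpoint, if 5.4 is followed as written?**

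| Endpoint | Local recurrence | Distant-only, before month 9 | Distant-only, after the month-9 CT |
|---|---|---|---|
| Local failure free survival at 9 months | Nothing: the event is observed | Month-9 local status | Nothing |
| Overall survival | No provision after recurrence | No provision | No provision |
| Late toxicity | No provision after recurrence | No provision | No provision |

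**3. Does another section fill the gap?**
- Section 8.1 counts death as a serious event only while the patient is under protocol surveillance. It also removes death from progression from safety reporting, because it belongs to efficacy. For a recurrent patient, 5.4 has already closed the efficacy schedule.
- Section 6.4 allows further analyses 5 years after the last inclusion, and 6.5 promises to report all included patients. Neither schedules any collection after recurrence.

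**4. The plan's own figure.** Section 6.2 gives 57 patients. That number is reproduced by a 90% confidence interval with a half-width of 10 points around 70%: n = 1.645² × 0.70 × 0.30 / 0.10² = 56.8, rounded up to 57. The calculation contains no allowance for patients without a 9-month status. The figure of 57 is not in dispute here and serves only to set the scale.

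**5. Illustrative bias if the exits were dropped.** Let f be the share lost, e the rate among those retained and d the shortfall in the rate among the lost. The rate in all patients is (1 − f)e + f(e − d) = e − f·d, so the retained rate is too high by f·d. The protocol gives neither f nor d; both are assumed.

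| f (assumed) | d (assumed) | f × d |
|---|---|---|
| 10% | 20 points | 2 points |
| 15% | 35 points | 5.25 points |
| 25% | 40 points | 10 points |

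Cross-check: with a true rate of 70%, 20% lost and a rate of 50% among the lost, the retained rate is (0.70 − 0.20 × 0.50) / 0.80 = 75%. The shortfall is then 75 − 50 = 25 points, and 0.20 × 25 = 5 points, which agrees.

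**6. Bounds without assuming a direction.** Suppose 80% of evaluable patients are local failure free. The rate in all 57 lies between 0.80(1 − f), if every lost patient failed, and 0.80(1 − f) + f, if none did.

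| f (assumed) | Evaluable of 57 | Bounds |
|---|---|---|
| 10% | 51.3 | 72% to 82% |
| 15% | 48.5 | 68% to 83% |
| 20% | 45.6 | 64% to 84% |
| 30% | 39.9 | 56% to 86% |

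The lower bound reaches the historical 70% at f = 1 − 0.70/0.80 = 12.5%, about 7 of 57 patients.

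**The case against.** The strongest reply is that 5.4 ends a visit schedule and not the patient's place in the trial. Several points follow, and much of this stands.

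- **Intention to treat.** A reader might infer that 5.4 contradicts 6.1. It does not: 6.1 fixes who is analysed, not how long they are assessed. Stopping assessment excludes no one. It weakens the principle by creating missing data.
- **Survival.** A reader might infer that deaths after recurrence are lost for good and overall survival cannot be estimated. That goes too far. Patients remain under local care, vital status needs no scheduled visit, and 8.1 treats death from progression as an efficacy matter. What can be said is that the protocol does not provide for its collection.
- **Appendix 4.** A reader might infer a second exit from follow-up for grade 4 toxicity. The entry stands in a drug-dosage column, 3.3 pauses the drug while radiotherapy goes on, and 8.3 ends only the drug. No section ends follow-up when the drug stops, and nothing marks these patients as having the worst prognosis. What remains is ambiguity: 5.4 makes leaving the study the trigger for local-standard follow-up, so a site could misread the entry.
- **Bias.** No rule to drop or censor is stated, and that choice may properly lie in the analysis plan. The product f·d describes dropping. Under censoring, patients contribute time until exit and the size differs. Patients leaving with distant-only disease are free of local failure at that moment, so a shortfall of 35-40 points would have to arise between exit and month 9. Even the sign is therefore plausible rather than proven. How the historical 70% treated distant relapse is not described; if it did so in the same way, part of the bias would cancel.

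The reply does not remove the core point. An analysis plan can choose how to handle missing values, but it cannot supply a CT that the protocol told the site not to schedule.

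**Conclusion.** The point holds within limits. Read plainly, 5.4 stops scheduled assessment at recurrence of any site. The primary endpoint loses its month-9 assessment only for distant-only recurrence before month 9. Overall survival and late toxicity lack any collection rule after every recurrence. This is more than missing detail, because the stated rule itself creates the gap, and the missing data are likely to be informative.

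The amount of bias is unknown, since no exit rate is given. The 2-10 points against a 10-point target are an illustration that rests on assumed f of 10-25%, assumed d of 20-40 points, and dropping as the way of handling exits. The bounds need no assumption about direction: with 80% observed among evaluable patients, a loss of more than 12.5% would leave a rate below 70% possible. Appendix 4 is a separate matter of wording and adds nothing to these figures.

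**What to change.** In 5.4, replace the clause that ends follow-up at recurrence with wording to this effect: *all included patients, whatever their distant recurrence, new therapy or stopping of study drug, keep the scheduled CT of the thorax through month 9 or until local failure, and are followed for vital status and late toxicity to 5 years.*

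Separately, reconcile the grade 4 entries in Appendix 4 with sections 3.3, 8.3 and 5.4. State whether the entry means the study drug or the study, and that stopping the drug does not end follow-up. Which dosing rule should apply is a clinical matter and outside this point.

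The cost is a short amendment, a few CTs in patients with distant relapse that are already in the schedule, and checks of vital status and late toxicity after recurrence. The sample size stays at 57.
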